2.4. Rationale for the Study

As outlined in Section 2.1, the ability to engineer a modified strain of nonpathological bacteria (*EcN* with DAP and thymidine [THY] auxotrophies, and no antibiotic resistance genes) with the ability to deliver a STING agonist (c-di-AMP) that is active only under hypoxic conditions (like a tumor, not in normal tissue or blood) is a strategy that combines both the known stimulation of the innate immune system with a target important to the release of Type 1 IFN.

This rationale lends support to the investigation of i.t. administration of SYNB1891, which in preclinical studies in mouse tumor models, is taken up by APCs leading to CDN production, STING activation and the release of type 1 interferons (IFN- α 1 and IFN- β 1). In addition, chassis-mediated engagement of PRRs on APCs (through for example the interaction of bacterial-derived LPS with its cognate receptor TLR4) further stimulates innate immunity. This ability of SYNB1891 to dually activate the innate immune system subsequently promotes the initiation of antitumor immune responses in the injected tumor, as well as the demonstration of long-term immunological memory.

The strategy of the current clinical development plan for SYNB1891 is based on an initial priming of the tumor microenvironment with SYNB1891, followed by targeted checkpoint inhibition with atezolizumab administered concurrently in continuous cycles to induce an optimal tumor response. Agonism of the STING pathway (and other PRRs) by SYNB1891 will lead to productive T cell priming and trafficking, but sustained antitumor activity is likely to require inhibition of the PD-1/PD-L1 pathway to address the T cell "exhaustion" that develops after priming. Therefore, the scientific rationale underlying the combination of SYNB1891 with atezolizumab is to stimulate multiple components of the immune response to cancer; innate immune activation, effector T cell activation, reinvigorating exhausted tumor-associated T cells, and prevention of further T cell exhaustion.

Study SYNB1891-CP-001 represents the first clinical study of SYNB1891. As such, a modified toxicity probability interval (mTPI) dose-finding algorithm (Ji et al 2013) will be implemented to determine the maximum tolerated dose (MTD) of single-agent therapy with SYNB1891 and recommended Phase 2 dose (RP2D) of SYNB1891 in combination with atezolizumab in patients with advanced/metastatic solid tumors or lymphoma. In preclinical toxicology studies, SYNB1891 was well tolerated in mice at doses up to 4.7×10^7 live cells per dose, which was considered to be the HNSTD of SYNB1891. This HNSTD is 47 times higher than the proposed starting dose of SYNB1891 (1×10^6 live cells/dose) in this first-in-human Phase 1 study. Upon demonstration of tolerability in accordance with the mTPI algorithm, the dose of SYNB1891 in Arm 1 will be subsequently escalated in approximately 3-fold increments.

After all patients in Arm 1 Cohort 4 have completed their Cycle 1 DLT safety evaluation, Arm 2 will investigate SYNB1891 starting at the Arm 1 Cohort 3 dose level, when given in combination with atezolizumab (1200 mg IV Q3W) in patients with advanced/metastatic solid tumors or lymphoma. Although the primary purpose of the study is to define the MTD/RP2D of study treatment, the broad patient population and standard frequency of disease assessments (every 2 cycles on treatment) may also enable the evaluation of any preliminary clinical activity elicited by the single-agent and/or combination regimens.

3. STUDY OBJECTIVES AND ENDPOINTS

The overall objective is to evaluate the safety and tolerability of escalating doses of i.t. injections of SYNB1891 to determine the single-agent MTD as monotherapy and the RP2D in combination with atezolizumab.

3.1. Primary

Incidence of dose-limiting toxicities (DLTs): Percentage of patients who experience a DLT

3.2. Secondary

Secondary objectives include evaluation of the following:

- Nature, incidence, and severity of all adverse events (AEs) and SAEs according to the National Cancer Institute (NCI) Common Terminology Criteria for Adverse Events (CTCAE), version 5.0
- Objective response rate (ORR) in target lesions as determined by the Response Evaluation Criteria in Solid Tumors, version 1.1 (RECIST 1.1) ([Eisenhauer et al 2009](#)), immune-related RECIST (iRECIST) ([Seymour et al 2017](#)), and/or the Lymphoma Response to Immunomodulatory Therapy Criteria (LYRIC) ([Cheson et al 2016](#)), with evaluations of the SYNB1891-injected tumor(s) and an overall response of up to 5 noninjected target lesions

3.3. Exploratory

Exploratory objectives include evaluation of the following:

- Duration of response or time to progression for evaluated tumors as determined by RECIST 1.1, iRECIST, and/or LYRIC
- Pharmacodynamic (PD) response biomarkers including tumor-infiltrating lymphocytes (TIL) characterization, immunomodulatory cytokine gene expression and IFN β responsive genes to be monitored in proximal and (if available) distal lesion biopsies at baseline and on study; systemic PD effects will be evaluated by assessment of changes in serum cytokine levels (including but not limited to tumor necrosis factor α [TNF α], interleukin [IL] 2, IL-4, IL-6, IL-8, IL-10, IL-12p70, IL-13, IL1 β , IL 1 receptor antagonist [IL1RA], IL 2 receptor alpha [IL2Ra], and IFN γ) at baseline and while on study
- Kinetics of SYNB1891 within the injected tumor will be assessed by quantitative polymerase chain reaction (qPCR) from predose (baseline) to predose Cycle 1 Day 8 from a fine needle aspirate (FNA); systemic kinetics of SYNB1891 will be monitored by qPCR from blood at predose (baseline) and 6 hours and 24 hours postdose in Cycle 1

4. STUDY DESIGN

4.1. Study Design Overview

This Phase 1, open-label, multicenter, 2-arm study will be conducting using the mTPI dose-finding design ([Ji et al 2013](#)). Cohorts of patients will be enrolled to receive escalating doses of SYNB1891 administered by i.t. injection until the target DLT range (approximately 30%) for SYNB1891 monotherapy is determined based on DLTs observed in Cycle 1 (Arm 1). The dose selected as achieving the target DLT range will be considered the MTD. After all patients in Arm 1 Cohort 4 have completed their Cycle 1 DLT safety evaluation, Arm 2 will enroll its first cohort starting at the Arm 1 Cohort 3 dose level, with SYNB1891 administered by i.t. injection in combination with atezolizumab administered as an intravenous (IV) infusion at a dose of 1200 mg every 3 weeks (Q3W) until the RP2D for the combination regimen is determined (see [Figure 4](#)).

The mTPI algorithm (as further discussed in Section [4.2.3](#)) will be implemented separately in each arm.

Eligible patients will be enrolled sequentially and will receive the first dose of study treatment within 28 days of screening.

Safety will be monitored continuously by documentation of AEs, SAEs, clinical laboratory measurements, vital signs, and physical examinations. DLTs, as defined in Section [4.2.4](#), will be evaluated through the end of the first cycle.

Disease status will be assessed by the local Investigator using appropriate imaging every 2 cycles for the duration of study treatment administration to evaluate the SYNB1891-injected lesion(s) and an overall response of up to 5 noninjected target lesions in accordance with RECIST 1.1 ([Eisenhauer et al 2009](#) and [Appendix 1](#)), iRECIST ([Seymour et al 2017](#) and [Appendix 2](#)), and/or LYRIC ([Cheson et al 2016](#) and [Appendix 3](#)).

Tumor biopsies and blood samples will be collected at baseline and at prespecified time points on study to evaluate the pharmacokinetics (PK), as measured by qPCR bacterial kinetics, and PD effects of study treatment.

Figure 4: SYNB1891-CP-001 Study Design

[figure not shown]
Arm 1: SYNB1891 monotherapy:

- Safety and tolerability to determine single agent MTD
- Proof of mechanism by exploratory pharmacodynamic (PD) biomarkers
- mTPI dose escalation; enroll up to 28 patients

Arm 2: SYNB1891 combination with CPI:

- Safety and tolerability
- Proof of mechanism by exploratory biomarkers
- Enroll up to 20 patients, with potential to enroll up to 20 in extension

SYNB1891-CP-001 Study Design

Abbreviations: CPI = checkpoint inhibitor; DLT = dose-limiting toxicity; MTD = maximum tolerated dose; mTPI = modified toxicity probability interval; RP2D = recommended Phase 2 dose; SRC = Safety Review Committee

4.2. Study Dosing Regimens

4.2.1. Treatments Administered

Patients enrolled to Arm 1 may receive up to four 21-day cycles of SYNB1891 monotherapy. On Days 1, 8, and 15 of Cycle 1 and Day 1 of Cycles 2 through 4, patients will receive an i.t. injection of SYNB1891 into an eligible lesion. If the initial eligible lesion undergoes complete regression and is no longer injectable (at the discretion of the Investigator), a subsequent eligible lesion (until no more eligible lesions remain) may be injected.

At the end of Cycle 4, patients in Arm 1 who do not have progressive disease (i.e., those who achieve and sustain complete response [CR], partial response [PR], or stable disease [SD]) may receive additional cycles of SYNB1891 administered by i.t. injection on Day 1 of each cycle for up to 24 months (i.e., Cycles 5 to 35) after the initial dose of study treatment until documentation of progressive disease or other discontinuation criteria, satisfaction of a predefined study stopping rule, or no eligible lesions remain.

Patients enrolled to Arm 2 may receive up to four 21-day cycles with SYNB1891 administered by i.t. injection into an eligible lesion on Days 1, 8, and 15 of Cycle 1 and Day 1 of Cycles 2 through 4. In addition, atezolizumab will be administered in accordance with its recommended dose and schedule (1200 mg IV Q3W) on Day 1 of each of the 4 planned cycles. On days when atezolizumab and SYNB1891 are both administered, SYNB1891 will be administered first, followed by at least 1 hour of observation prior to the atezolizumab infusion. Patients in Arm 2 who do not have progressive disease (i.e., those who achieve and sustain CR, PR, or SD) at the end of Cycle 4 on combination therapy may receive additional cycles of SYNB1891 and atezolizumab for up to 24 months (i.e., Cycles 5 to 35) after the initial dose of study treatment until documentation of progressive disease or other discontinuation criteria, satisfaction of a predefined study stopping rule, or no eligible lesions remain.

Locating and/or injecting the lesion may be performed using guided imaging at the discretion of the Investigator.

4.2.2. Postdose Monitoring

The initial patient in each Arm 1 cohort (Sentinel patient) will be monitored for at least 6 hours following the first (Cycle 1 Day 1) i.t. injection of SYNB1891 (or overnight, at the discretion of the Investigator) for evaluation of any procedural complication or acute toxicity (i.e., injection reactions or cytokine release syndrome) and for collection of postdose blood samples. Safety data must be reviewed on or after Day 7 and deemed acceptable by the Investigator and the Sponsor and contract research organization (CRO) Medical Monitors before the Sentinel patient receives any further injections and before any subsequent patients are dosed in that cohort.

For the remainder of Cycle 1 dosing for the Sentinel patient and for all dosing for non-Sentinel patients, SYNB1891 injections will be administered in the outpatient setting and patients will be closely observed at the clinic for at least 6 hours following each injection for evaluation of any procedural complication or acute toxicity (i.e., injection reactions or cytokine release syndrome) and for collection of postdose blood samples. All patients will be contacted by telephone on Cycle 1 Day 3 to monitor for signs of cytokine release syndrome (see Section 4.4).

4.2.3. Dose-finding with the mTPI Algorithm

In both study arms, each cohort will initially comprise 3 patients (a Sentinel patient and 2 non-Sentinel patients), with subsequent dose escalation governed by an mTPI design (Ji et al 2013).

The starting dose of SYNB1891 in the first cohort of Arm 1 will be 1×10^6 live cells and will be increased in approximately 3-fold increments in subsequent cohorts until MTD determination. If no MTD is identified, then the MTD will be considered the maximum dose at which a sufficient number of patients have been treated such that if 14 patients were administered that dose then either escalation or staying at the current dose would be recommended according to [Table 1](#). For example, if 8 patients were administered a dose level with 0 DLTs observed, even if all remaining 6 patients had a DLT, [Table 1](#) would indicate “stay at the current dose”; thus, the remaining 6 patients are not required to evaluate the MTD.

A mTPI design with a target DLT rate of approximately 30% will be applied for dose escalation and confirmation to determine the MTD/RP2D. In Arm 1, predetermined dose levels of 1×10^6 , 3×10^6 , 1×10^7 , 3×10^7 , 1×10^8 , 3×10^8 , and 1×10^9 live cells will be explored independently, with additional dose levels as necessary to determine the MTD. A de-escalation dose of 3×10^5 live cells is available if the starting dose is deemed not tolerable. All dose escalation and de-escalation decisions will be based on the occurrence of DLTs at a given dose during Cycle 1 and will be made jointly by the Investigators and the Sponsor.

In [Table 1](#), the number of patients treated is indicated in the columns and the number of patients who experienced a DLT is indicated in the rows. Dosing decisions include escalate to the next higher dose (E), stay at the current dose (S), de-escalate to the next lower dose (D), and de-escalate to a lower dose and never test this dose again (i.e., unacceptably toxic dose; DU). During dose escalation, a minimum of 3 patients are required at each dose. Depending on accrual rate and occurrence of DLTs, 3, 4, 5 or 6 patients may be enrolled at each new dose until the last of those patients completes the Cycle 1 DLT assessment period. For example, the dose escalation rules will proceed as follows if 3 patients are enrolled: if 0 of the first 3 patients at a given dose level develops a DLT, then the dose can be escalated to the next level without further expansion. If 1 of the first 3 patients at a given dose level develops a DLT, no more than an additional 3 patients should be enrolled at this dose level until additional DLT data are available since this dose would be considered unacceptably toxic if all 3 of the additional patients experience a DLT (i.e., 4 of 6 patients). If 2 of the first 3 patients at a given dose level develop a DLT, the dose will be de-escalated to the next lower level. If 3 of the first 3 patients at a given dose level develop a DLT, this dose will be considered unacceptably toxic (i.e., the dose will be de-escalated and never re-escalated to that dose again). The same principle will be applied whether 3, 4, 5 or 6 patients are enrolled in the same dose cohort according to [Table 1](#).

Based on the mTPI design, the number of patients who are enrolled at a dose, but are not yet fully evaluable for DLT assessment, may not exceed the number of remaining patients who are at risk of developing a DLT before the dose would be considered unacceptably toxic (denoted as DU in [Table 1](#)). To determine how many more patients can be enrolled at a dose level, one can count steps in a diagonal direction (down and to the right) from the current cell to the first cell marked DU. In total, 3 to 14 patients may be enrolled at a given dose level.

Dose escalation and confirmation will end after 14 patients have been treated at any of the selected doses. The pool-adjacent-violators-algorithm (Ji et al 2013) will be used to estimate the

- Review of the safety data for the first patient in a cohort (Sentinel patient) must be completed on or after Day 7 before the remaining 2 patients (non-Sentinel) in that cohort may be dosed (these 2 patients may be dosed concurrently). Observation of DLT(s) in a Sentinel patient will not necessarily preclude enrollment of subsequent

patients at the same dose level; rather, DLTs occurring in Sentinel patients will be reviewed individually by the SRC (consisting of the Sponsor Medical Monitor, the CRO Medical Monitor, all active Investigators, and other study personnel as needed) to determine appropriate dosing for subsequent patients.

- After all patients in a cohort have been assessed for DLTs (i.e., after each patient either experiences a DLT or completes the end of Cycle 1 safety assessment, whichever occurs first), the SRC will review all available safety data from the cohort and determine whether to escalate to the next higher SYNB1891 dose, enroll additional patients at the current dose, de-escalate to the next lower dose, or declare that the study objectives or stopping rules have been met. The decision will be informed by the mTPI algorithm recommendation to achieve the targeted toxicity interval.
- Patients must either experience a DLT during Cycle 1 or receive at least 2 of the 3 planned SYNB1891 injections to be considered evaluable for DLT evaluations and contribute to dose-escalation decisions for a given cohort. Patients who withdraw from the study for any reason other than DLTs prior to receiving the second injection of SYNB1891 in Cycle 1 may be replaced.

Once the RP2D of Arm 2 is determined, up to 20 additional patients may be enrolled in the RP2D cohort to fully characterize the safety profile of SYNB1891 in combination with atezolizumab.

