4.2.4. Definition of Dose-limiting Toxicity

The occurrence of any of the following toxicities during Cycle 1 will be considered a DLT, if assessed by the Investigator to be possibly, probably, or definitely related to study treatment administration.

1. Grade 4 nonhematologic toxicity (not laboratory)
2. Grade 4 hematologic toxicity lasting \geq 7 days, except thrombocytopenia:
 - Grade 4 thrombocytopenia of any duration
 - Grade 3 thrombocytopenia associated with clinically significant bleeding
3. Any nonhematologic AE Grade \geq 3 in severity should be considered a DLT, with the following exceptions: Grade 3 fatigue lasting \leq 3 days; Grade 3 diarrhea, nausea, or vomiting without use of antiemetics or antidiarrheals per standard of care; Grade 3 rash without use of corticosteroids or anti-inflammatory agents per standard of care
4. Any Grade 3 or Grade 4 nonhematologic laboratory value if:
 - Clinically significant medical intervention is required to treat the patient, or
 - The abnormality leads to hospitalization, or
 - The abnormality persists for $>$ 1 week, or
 - The abnormality results in a drug-induced liver injury (DILI)
 - Exceptions: clinically nonsignificant, treatable, or reversible laboratory abnormalities including liver function tests, uric acid, etc.
5. Febrile neutropenia Grade 3 or Grade 4:

- Grade 3 is defined as absolute neutrophil count (ANC) $< 1000/\text{mm}^3$ with a single temperature of $> 38.3^\circ\text{C}$ (101°F) or a sustained temperature of $\geq 38^\circ\text{C}$ (100.4°F) for more than 1 hour
- Grade 4 is defined as ANC $< 1000/\text{mm}^3$ with a single temperature of $> 38.3^\circ\text{C}$ (101°F) or a sustained temperature of $\geq 38^\circ\text{C}$ (100.4°F) for more than 1 hour, with life-threatening consequences and urgent intervention indicated

6. Sepsis, severe abscesses and/or ulcerations requiring surgical management
7. Prolonged delay (> 2 weeks) in initiating Cycle 2 due to treatment-related toxicity
8. Investigator decision to discontinue study treatment for a treatment-related toxicity during Cycle 1
9. Missing $> 33\%$ of study drug doses as a result of Grade 3 drug-related AE(s) during the first cycle
10. Grade 5 toxicity

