4.3.1. Dosing Delays and Interruptions

Study treatment dosing delays will be permitted in any treatment cycle if unforeseen circumstances prevent the patient from returning to the clinic on the scheduled day(s). A maximum delay of 2 days in Cycle 1 will be permitted. If administration of study treatment is delayed by > 2 days in Cycle 1, that dose is considered missed and the patient should receive the next dose at the next visit.

If a patient misses ≥ 2 SYNB1891 doses in Cycle 1, then the patient will be discontinued permanently from treatment and may be replaced (see Section 8.2.1). In Cycle 2 and beyond, if a patient misses the dose of SYNB1891, then the patient may be discontinued permanently from treatment, unless the Investigator's assessment of the benefit/risk suggests otherwise (after consultation with Sponsor). If treatment is permanently discontinued, patients will continue to be followed for safety as indicated for end of treatment and follow-up.

SYNB1891 treatment interruption can occur due to treatment-related toxicity, including Grade 3 or higher infections or local inflammation requiring antibiotics, and the start of a new cycle may not occur until the following criteria have been met:

- Nonhematologic toxicities have returned to either baseline or Grade ≤ 1 , or at the Investigator's discretion, Grade ≤ 2 if not considered a safety risk. This condition must be met within 14 days of the initial treatment interruption.
- Hematologic toxicities: ANC $\geq 1000/\text{mm}^3$ or have returned to baseline levels; platelet count $\geq 50,000/\text{mm}^3$ or has returned to baseline levels. This condition must be met within 14 days of the initial treatment interruption.
- If a patient requires treatment with a systemic antibiotic on study, SYNB1891 should be held for the duration of the antibiotic regimen and for 5 half-lives after the last dose of antibiotics. Once the patient is apyretic after completion of the antibiotic washout period, SYNB1891 may resume.

If the patient cannot meet the above conditions within the specified time frame, then study treatment should be permanently discontinued, unless the Investigator's assessment of the benefit/risk suggests otherwise (after consultation with Sponsor). The patient may be replaced (see Section 8.2.1).

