7.2.5. Clinical Laboratory Measurements

Clinical laboratory tests will be performed (predose unless otherwise specified) at the time points indicated in [Table 19](#) and [Table 20](#). Baseline laboratory measurements do not need to be repeated if screening measurements were performed within 3 days prior to Cycle 1 Day 1.

Screening for HIV and hepatitis B and C will also be performed prior to study dosing. Serum pregnancy testing will be performed at screening, with urine pregnancy testing performed at subsequent time points (see [Table 19](#) and [Table 20](#)).

Screening results will be assessed by the Investigator for inclusion of patients in the study. Additionally, unscheduled clinical laboratory tests can be obtained at any time during the study

at the Investigator's discretion. The diagnosis corresponding to any clinically significant abnormality, or abnormality requiring treatment/intervention, must be recorded as an AE.

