7.2.5.1. Local Laboratory Measurements

[Table 17](#) outlines the clinical laboratory measurements that will be reviewed at the local laboratory.

On dosing days, prior to receiving study treatment, patients must meet the laboratory value criteria outlined in Section [5.2.1.1](#), with the exception that platelets may be $\geq 75,000/\mu\text{L}$ without transfusion and hemoglobin may be $\geq 8.5 \text{ g/dL}$ (patients may be transfused to meet this criterion).

Table 17: Local Laboratory Parameters

Panel	Parameters	
Hematology	Must be Reviewed Pre-dose:	
	Calculated absolute neutrophil count	
	White blood cell	Neutrophils
	Red blood cell	Lymphocytes
	Red cell indices	Monocytes
	Hemoglobin	Eosinophils
	Hematocrit	Basophils
	Platelet count	
Chemistry	Must be Reviewed Pre-dose:	
	Calcium	Alkaline phosphatase
	Chloride	Aspartate aminotransferase
	Total protein	Alanine aminotransferase
	Potassium	Lactate dehydrogenase
	Glucose	Direct bilirubin
	Sodium	Indirect bilirubin
	Blood urea nitrogen	Total bilirubin
	Creatinine	
	Bicarbonate	
	Albumin	
	Uric acid	
	Phosphorus	
	Magnesium	
Thyroid Function	May be Reviewed Pre- or Postdose:	
	Free T4	Thyroid-stimulating hormone
Coagulation	May be Reviewed Pre- or Postdose:	
	Prothrombin time and/or activated partial thromboplastin time	
	International normalized ratio	
Urinalysis	May be Reviewed Pre- or Postdose:	
	Dipstick:	Microscopic (if dipstick is positive):
	pH	White blood cell count
	Glucose	Red blood cell count
	Protein	Casts
	Bilirubin	
	Ketones	
	Leukocytes	
	Blood	

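### The Sentinel review may release two more patients on Day 7, but the first scheduled post-dose blood count, chemistry and coagulation draw is Day 8 ± 1

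*Protocol*

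**What the plan says.** Protocol 4.2.3 lists enrollment rules for both arms. Under the first, review of the first patient's safety data "must be completed on or after Day 7 before the remaining 2 patients (non-Sentinel) in that cohort may be dosed"; the two may then be dosed concurrently.

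Protocol 4.2.2 sets the same earliest day: "Safety data must be reviewed on or after Day 7 and deemed acceptable by the Investigator" and by the Sponsor and CRO Medical Monitors, "before the Sentinel patient receives any further injections and before any subsequent patients are dosed in that cohort". That paragraph is written for Arm 1: "The initial patient in each Arm 1 cohort (Sentinel patient) will be monitored for at least 6 hours".

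Neither section lists the data the review must include.

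Tables 19 and 20 schedule hematology, chemistry/LFTs and coagulation at screening, at Day 1 predose and next at Day 8 ± 1. SAP Appendix 3 shows the same draw days.

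Protocol 7.2.5.1 adds a condition for each patient's own dosing: "On dosing days, prior to receiving study treatment, patients must meet the laboratory value criteria outlined in Section" 5.2.1.1, relaxed to platelets of at least 75,000/µL and hemoglobin of at least 8.5 g/dL. Protocol 7.2.5 also says that "unscheduled clinical laboratory tests can be obtained at any time during the study", at the Investigator's discretion.

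**The concern.** The Sentinel step is there so that one patient shows what a dose level does before two more receive it. This is the first human study of a live bacterial product. The three highest planned Arm 1 levels (1×10^8, 3×10^8 and 1×10^9 cells) exceed the mouse highest nonseverely toxic dose of 4.7×10^7 in absolute cells, without scaling between species.

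If the review closes on Day 7, the reviewers may have no post-dose platelet count, liver test or clotting result. Some dose-limiting toxicities can be seen only in those results: Protocol 4.2.4 counts "Grade 4 thrombocytopenia of any duration", so a single count can establish one. Under 4.2.3, Sentinel DLTs go to the Safety Review Committee, which decides dosing for later patients. A DLT that has not been measured cannot reach it.

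The plan is also uneven here. It requires current laboratory results before the Sentinel is injected again, but not before two new patients receive the same level. Two patients could be dosed on Day 7 and the Sentinel's own injection withheld on Day 8 for low platelets.

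**Working it through.** No sample-size or error-rate figure is involved. The check compares the earliest release day with the draw days.

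**1. Scheduled Sentinel data between the Day 1 injection and the Day 8 visit** (Tables 19 and 20; same pattern in both arms)

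| Assessment | 6 h | Day 2 (24 h) | Day 3 | Day 8 ± 1 |
|---|---|---|---|---|
| Hematology | – | – | – | yes (predose) |
| Chemistry/LFTs | – | – | – | yes (predose) |
| Coagulation | – | – | – | yes |
| Cytokines | yes | yes | – | yes |
| Blood qPCR | yes | yes | – | – |
| Vital signs | yes | yes | – | yes |
| Physical examination | – | yes | – | yes |
| Telephone call | – | – | yes | – |

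Scheduled post-dose draws before the Day 8 visit number 0 for hematology, chemistry and coagulation, and 2 each for cytokines and blood qPCR. Cytokines and qPCR are central-laboratory tests (Table 18). Nothing requires their results by Day 7, and they do not replace a platelet count or liver tests.

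**2. Release day against draw day**

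- Earliest release: Day 7.
- Permitted Day 8 visit: 8 − 1 to 8 + 1 = Days 7, 8 or 9.
- With a Day 7 release, the panel follows the release if the visit is on Day 8 or 9, which is 2 of the 3 permitted days. If the visit is on Day 7, the panel helps only if it is resulted before the review closes. This counts days and is not a probability.

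**3. Which way the rules push the review**

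In Arm 1 the same review must precede the Sentinel's second injection, due at that visit. This favors a review on Day 7, or on Day 8 before injection. The panel is itself a predose draw at that visit, so the two events fall close together with no stated order.

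**4. How often the situation arises**

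- Planned cohorts (Protocol 5.1): 4 + 1 = 5 to 7 + 5 = 12.
- Patients released by such a review: 2 × 5 = 10 to 2 × 12 = 24.

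These are opportunities for the gap, not expected occurrences.

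**5. Delay if release waits for the panel**

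- Per cohort against a Day 7 release: 7 − 7 = 0, 8 − 7 = 1 or 9 − 7 = 2 days, plus turnaround (not stated).
- Arm 1: 7 × 2 = 14 days at most. Arm 2: 5 × 2 = 10 days at most. The arms can overlap in time.
- If the 2-day Cycle 1 dosing delay in 4.3.1 put the visit on Day 10, the wait would be 3 days for that cohort.

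**The case against.** The strongest reply is that the schedule fits the Sentinel's stated purpose. Protocol 4.2.2 looks for procedural complications and acute toxicity, and the events of special interest in 9.3 are cytokine release, systemic infection and local reactions. Vital signs, the Day 2 examination, the Day 3 call and continuous AE monitoring cover these, and the documents cite no SYNB1891 signal of silent marrow or liver toxicity. Release also needs active agreement by the Investigator and two Medical Monitors, whose remit in 9.7 includes laboratory data. They may wait a day or order a panel, and 4.5 lets them stop enrollment.

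The consequence is also bounded:

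- Under 4.2.4, a Grade 3/4 liver value is a DLT only with further conditions, and platelets below 75,000/µL hold a dose without being a DLT.
- A Sentinel DLT does not automatically stop enrollment.
- Results would normally arrive before the released patients' second injections, so the avoidable exposure is about one SYNB1891 injection each.
- Arm 2 runs at least one SYNB1891 level below the dose under evaluation in Arm 1.

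All of this stands as a limit on weight. A Day 8 panel would often flag a problem rather than classify it. But every safeguard named is discretionary or protects a different patient. None makes a post-dose blood count or chemistry result a condition of release, and the reviewers can judge only the data they have.

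**Conclusion.** The concern holds. A site can follow 4.2.2, 4.2.3 and the schedule exactly and still dose two more patients with no post-dose hematology, chemistry or coagulation result from the Sentinel.

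This requires the review to close on Day 7, or at any rate before the panel is resulted, with no unscheduled test ordered. The documents do not show how often that would happen. The harm at stake is limited to clinically silent laboratory toxicity, and to roughly one injection in each of two patients per release. The change is worth making because the data are already scheduled a day or so later and waiting costs little against a 21-day DLT period.

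**What to change.** In 4.2.3, and in the matching release wording of 4.2.2, state that non-Sentinel patients may be dosed only after the Sentinel's Day 8 (± 1) predose hematology and chemistry/LFT results have been reviewed, with coagulation when available. If the Day 8 visit is missed or falls outside its window, draw an equivalent unscheduled panel on or after Day 7. Merely asking the review to include available Day 8 results would not close the gap, since none need be available on Day 7.

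Keep the Sentinel's second injection under the existing Day 7 review and the predose criteria in 7.2.5.1. This matters because, under 4.3.1, "If administration of study treatment is delayed by > 2 days in Cycle 1, that dose is considered missed", and evaluability needs at least 2 of the 3 injections unless a DLT occurs.

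**Cost.** There is no new scheduled sample. Table 17 already requires predose review of hematology and chemistry; coagulation may be reviewed after dosing, hence the softer requirement for it. Release moves by the 0 to 2 days worked out above, plus turnaround. Where the Sentinel review has closed before the panel is back, a short second sign-off by the same parties is needed. Where it is held at the Day 8 visit with results in hand, one review serves both purposes. A missed visit costs one unscheduled panel.

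As a separate clarification, 4.2.2 should say whether the hold on the Sentinel's own further injections also applies in Arm 2.
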